10.9 Analysis of Primary Endpoint

10.9.1 Recurrence Rate of UTI

The number (%) of subjects with any Symptomatic/Probable UTI (defined in Section 3.3) episode over the four-month study period will be assessed, as well as the number (%) of subjects with Symptomatic UTI. The number (%) in each treatment group will be presented. 95% confidence intervals will be calculated to evaluate any difference between the treatment groups.

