4.3 Rationale for Study Design

The study will enroll 276 pre-menopausal women currently with a symptomatic UTI who report at least one other symptomatic UTI episode treated within the past 12 months. Subjects will be randomized to receive either LACTIN-V (5×10^9 CFU/applicator) or a placebo applicator in a 1:1 ratio. The Randomization Visit (Visit 1) must occur within 3–

10 days of completing antibiotics since the vaginal microbiota is thought to be maximally disrupted at this time, thus providing *L. crispatus* CTV-05 the best chance of successful colonization.

It is not anticipated that the entry UTI episode will necessarily have fully resolved at the time of randomization (Visit 1), as mild symptoms may still be present, and the dipstick and urinalysis may still be positive or equivocal several days after completing antibiotics. However, the urine culture is anticipated to be negative at Visit 1, following completion of antibiotics; therefore, subjects with a positive urine culture at this visit will be considered an antibiotic treatment failure.

All subjects will return to clinic at 2, 4, 8, 12, and 16 weeks to assess efficacy and safety. Colonization with *L. crispatus* CTV-05 and other lactobacilli, as well as *E. coli*, will be assessed at all visits. Nugent scores will be determined at baseline and all subsequent visits to evaluate vaginal microbiota pre- and post-treatment.

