6.2.1.5 Discontinuation and Subject Replacement

The study subject may choose to leave the study at any time. Reasons for leaving the study will be recorded. Study subjects who enroll in the study but who do not return after three attempts to contact them will be considered study “lost to follow-up”.

Once a subject is randomized, she will not be replaced. Withdrawals and drop-outs will not be replaced.

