6.2.2 Blinding and Unblinding of Treatment Assignment

6.2.2.1 Blinding

The most important factor for the success of a blinded study is to maintain the blind throughout the entire course of the trial. In this study, the treatment assignment to LACTIN-V and the placebo applicator will be maintained by [name], M.S., the study statistician. Treatment assignment will be blinded to all other study staff and subjects.

The study product will be prepackaged in accordance with a previously generated randomization schedule. It will be supplied to the study site labeled only with the Protocol Number and Subject Number. As study product is shipped to the sites, a list of Subject Numbers that corresponds to the study product will be enclosed.

A block size of four has been chosen to minimize the potential imbalance between LACTIN-V and placebo. Within each block, subjects will be randomized in a 1:1 ratio to receive either LACTIN-V or placebo. Subjects will be randomized on site in sequential order based on the list of Subject Numbers provided to the site. Lists will not have any treatment assignment associated with the Subject Number.

Applicators will be individually packaged. No one involved in the conduct of the trial will be aware of the specific treatment allocated to any particular subject. Only authorized persons, including the study statistician, will have access to treatment assignments in case of necessary unblinding (see below). The LACTIN-V applicator cannot be distinguished from the placebo applicator (appearance or smell) either before or during administration.

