10.4 Statistical Power and Sample Size Justification

Based on previous studies in this population, we estimate that 40% of women with a history of rUTI and recent treatment for a UTI will have a recurrence within the 4 month follow-up period, based on data from a recently completed rUTI study at this site (17). We plan to enroll 250 women to allow for >80% power to detect a 50% reduction in UTI incidence, also factoring in some drop-out, non-compliance and loss-to-followup, plus a cushion in case of a recurrence rate of less than 40%.

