10.7 Cohorts for Analyses

The intent-to-treat (ITT) cohort is defined as subjects who are randomized in the study.

The modified intent-to-treat (MITT) cohort is defined as subjects who are randomized and have received at least one dose of study product. It is a subset of the ITT cohort. It will be used for analyses of primary and secondary endpoints, baseline characteristics, trial conduct, and significant protocol deviations.

The evaluable (Eval) cohort is defined as the subset of the MITT cohort who had at least one follow-up visit assessment post-baseline (Visit 2 or later) and are not an antibiotic treatment failure at Visit 1 (defined as a requiring treatment for UTI symptoms at Visit 1). Subjects with any significant protocol deviations may be included in this cohort.

The according-to-protocol (ATP) cohort is the subset of Eval with subjects who meet all protocol specifications. Those subjects who developed exclusion criteria while on study will be excluded from this cohort.

Both Eval and ATP cohorts will be used to analyze the primary endpoints.

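### Section 10.9.1 has no rule for women lost before the end without a UTI; the crude percentage in effect counts them as recurrence-free, which biases the arm comparison if loss is unequal

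*Combined protocol and SAP*

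**What the plan says.** Section 10.9.1 sets out the binary primary analysis: "The number (%) of subjects with any Symptomatic/Probable UTI (defined in Section 3.3) episode over the four-month study period will be assessed". The arms are compared by interval: "95% confidence intervals will be calculated to evaluate any difference between the treatment groups". Neither sentence gives a denominator or a rule for incomplete follow-up, and Section 10 has no missing-data rule for this endpoint.

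The denominators have to be taken from Section 10.7. The MITT cohort, which is used for the primary endpoints, is made up of women who are "randomized and have received at least one dose of study product", with no follow-up requirement. The Eval cohort, also used for the primary endpoints, requires one assessment at Visit 2 or later and removes antibiotic treatment failures at Visit 1. It does not require complete follow-up.

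Section 10.4 expects some drop-out and loss to follow-up but gives no figure. Section 6.2.1.5 adds: "Withdrawals and drop-outs will not be replaced". Section 10.9.3 plans Kaplan-Meier curves and a log-rank test for time to first UTI, but Section 10.9.1 does not use them for the percentage.

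**The concern.** A woman last seen at Week 3 without a UTI has most of her risk period unobserved. If the percentage is computed from the cohorts as defined, she adds one to the denominator and nothing to the numerator, which is the same as recording no recurrence over four months. Each arm's percentage is then biased low. If one arm loses more women, its percentage is pulled down further, and a difference can appear even when the product does nothing and loss is unrelated to UTI risk.

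This matters because the percentage is the first primary variable in Table 1 and is the quantity behind the sample size in Section 10.4. Section 10.1 lists three primary comparisons and makes none of them decisive, so the crude percentage could be reported as the main result.

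**Working it through.** **Inputs from the documents.**
- Recurrence risk, Section 10.4: "we estimate that 40% of women with a history of rUTI and recent treatment for a UTI will have a recurrence".
- Size and effect, Section 10.4: "We plan to enroll 250 women to allow for >80% power to detect a 50% reduction in UTI incidence", that is 40% against 20%.
- Allocation, Section 6.2.2.1: "subjects will be randomized in a 1:1 ratio to receive either LACTIN-V or placebo", so 125 per arm. Section 4.3 has another total: "The study will enroll 276 pre-menopausal women currently with a symptomatic UTI", which is 138 per arm.

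**Assumptions not in the documents.** Two-sided 5% level; all drop-out rates and their timing; constant hazards; loss unrelated to UTI risk. Type I error here means the chance, with no true effect, that the 95% interval excludes zero, because Section 10.9.1 names intervals and no test.

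**Step 1: the plan's own figure.** With p1 = 0.40, p2 = 0.20 and mean 0.30, n per arm = [1.960·√(2·0.30·0.70) + 0.8416·√(0.24 + 0.16)]² / 0.20² = (1.2702 + 0.5323)² / 0.04 = 81.2, so 82. With 125 per arm, power = Φ[(0.20·√125 − 1.2702) / 0.6325] = Φ(1.527) = 93.7%. If 15% of women are removed it is 89.5%, and if 30% are removed it is 82.9%. The claim of more than 80% holds.

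**Step 2: what the crude percentage estimates.** Let p be the true risk and d the probability of loss over the period. Put L = −ln(1 − p) and M = −ln(1 − d). The expected crude proportion is L/(L + M) × [1 − (1 − p)(1 − d)]. For p = 0.40, L = 0.5108:
- d = 10%: M = 0.1054, giving 0.8290 × 0.46 = 38.1%.
- d = 20%: M = 0.2231, giving 0.6960 × 0.52 = 36.2%.
- d = 30%: M = 0.3567, giving 0.5889 × 0.58 = 34.2%.

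**Step 3: type I error.** True risk 40% in both arms, 125 per arm, exact binomial calculation with the unpooled interval:

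| Loss, LACTIN-V / placebo | Crude %, LACTIN-V / placebo | Two-sided type I error |
|---|---|---|
| none | 40.0 / 40.0 | 5.1% |
| 6% / 4% | 38.9 / 39.3 | 5.3% |
| 8% / 4% | 38.5 / 39.3 | 5.4% |
| 10% / 4% | 38.1 / 39.3 | 5.7% |
| 20% / 10% | 36.2 / 38.1 (ratio 0.95) | 6.6% |
| 30% / 10% | 34.2 / 38.1 (ratio 0.90) | 10.6% |

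Equal loss leaves the null difference at zero. Its cost is dilution: with 15% loss in each arm, a true 20-point difference becomes 18.7 points and power falls from 94.0% to 91.8%.

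**Step 4: timing.** If all loss falls at Week 3 of 16, the crude proportion is (1 − d)·0.40 + d·(1 − 0.6^(3/16)), where the last bracket is 0.0913. At 20% / 10% loss this gives 33.8% against 36.9%, a spurious 3.1 points. By a normal approximation to the pooled test, type I error runs from 6.0% (loss spread evenly) to 8.0% (all at Week 3) for 20% / 10%, and from 9.2% to 17.7% for 30% / 10%. With 138 per arm, the 20% / 10% range is 6.1% to 8.3%.

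**Step 5: direction.** In the Step 4 calculations, false claims of benefit at 20% / 10% are 4.8% to 7.4%, against a nominal 2.5%. With the gap reversed (10% / 20%) they fall to 1.2% to 0.7%, and power for 40% against 20% is 86.8% to 79.6%.

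**Step 6: does the remedy work?** In 10,000 simulated trials per scenario (10/10, 20/10, 25/10 and 30/10% loss, spread evenly or at Week 3), censoring at last contact kept type I error at 5.1% to 5.7% for the Kaplan-Meier 16-week difference. The log-rank test gave 4.9% to 5.3%. The crude percentage in the same scenarios ran from 5.2% to 18.3%.

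**The case against.** The best defence is that the harm depends on a drop-out gap for which the documents give little support. The earlier trial of similar design (UW/LB-001, Section 2.2.2.2) randomized 50 per arm and analysed 48 per arm, so 4% were missing in each. Its only reported discontinuation for adverse effects was on placebo. Near that experience the excess type I error is under one percentage point. The protocol also limits loss: Section 6.2.1.4 continues efficacy follow-up after product is stopped, and Section 6.3.7 obtains records of UTIs diagnosed elsewhere. Women lost before Visit 2 are outside the Eval cohort. The log-rank analysis in Section 10.9.3 is also primary, and it is not affected when loss is non-informative.

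Most of this stands and limits the size of the point, but it does not supply the missing rule. The 48 of 50 are analysis denominators and do not show that follow-up was complete. In LV-003 (Section 2.2.2.2) several symptoms, among them vaginal discharge and odour, were at least 5 points more frequent on LACTIN-V, so unequal loss is plausible. The log-rank test does not estimate the percentage with a UTI.

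A reader might infer two stronger things. One is that the plan states that lost women are recurrence-free. It does not; this follows from the denominators. The other is that the false-positive rate is raised in general. It is not: the rise needs unequal loss, and false claims of benefit rise only if LACTIN-V is the arm that loses more.

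**Conclusion.** The point holds as a missing rule with a conditional bias. As defined, the crude percentage treats loss without a UTI as no recurrence in MITT, and in Eval once Visit 2 has been attended. Both percentages are then too low, and the comparison shifts if loss differs by arm. Type I error is about 5% with equal loss, 5.3% to 5.7% for gaps of 2 to 6 points, 6.6% at 20% against 10%, and 10.6% at 30% against 10%, and higher with early loss. If placebo loses more, false claims of benefit fall and power drops. These sizes rest on assumed drop-out rates, constant hazards, non-informative loss and a two-sided 5% level. The two enrolment totals (250 and 276) need reconciling, but the choice does not change the conclusion. The change should be made before the data are unblinded; the point does not by itself undermine the trial.

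**What to change.** In Section 10.9.1, estimate the percentage with a UTI in each arm as one minus the Kaplan-Meier estimate at the end of the study period, censoring women without a UTI at last contact. Report the difference between arms with its 95% confidence interval. State the time point: Section 10.1 speaks of 16 weeks, while Section 10.3 places Visit 6 at Week 18. Keep the crude count as a descriptive line. Add a tipping-point analysis that varies the assumed UTI risk of lost women, by arm, until the conclusion changes. State the corresponding rule for the episode counts in Section 10.9.2, which have the same gap.

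The cost is analysis wording only, since Section 10.9.3 already needs the dates and plans the curves. The downside is a slightly wider interval and a main estimate that relies on non-informative censoring. Loss driven by symptoms could break that assumption, which is why the tipping-point analysis is needed.

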10.9.2 Incidence of Symptomatic UTI episodes

The number of Symptomatic/Probable UTI (defined in Section 3.3) episodes per subject in each treatment group will be summarized by treatment group, as well as the number Symptomatic UTI episodes. Number and percent of subjects with 0, 1, 2, ..., n episodes will be displayed by treatment group. P-value will be calculated by CMH methods to evaluate any difference between the treatment groups.

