3.2 Study Objectives

3.2.1 Primary Objective

The primary objective of this study is to evaluate the efficacy of LACTIN-V, compared to placebo, in pre-menopausal women with recurrent uncomplicated UTI.

1. To evaluate the number (percent) of subjects in each treatment group with at least one recurrence of symptomatic UTI.
2. To evaluate the efficacy of LACTIN-V, compared to placebo, in reducing the incidence of symptomatic UTI.
3. To evaluate the time to recurrence, in subjects receiving LACTIN-V as compared to placebo, of symptomatic UTI

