10 STATISTICAL CONSIDERATIONS

10.1 Primary Endpoint

The primary endpoint of this Phase 2 study is to evaluate the efficacy of *Lactobacillus crispatus* strain CTV-05 (LACTIN-V) in pre-menopausal women who have a history of recurrent uncomplicated UTI when the product is administered vaginally at a dose of 2 x 10⁹ CFU/capsule once per day for five consecutive days followed by once per week for 10 weeks. The main analysis of interest will be the comparison of UTI during the follow-up period, looking at:

1. UTI incidence over the 16-week study period in the LACTIN-V treatment group (Group A) as compared to the placebo group (Group B) of:
 - a. Symptomatic or Probable UTI
 - b. Symptomatic UTI
2. Time to recurrence, as measured from date of the Randomization Visit (Day 1) to the date of first UTI diagnosis post-randomization, in the LACTIN-V group (Group A) compared to the placebo group (Group B) of:
 - a. Symptomatic or Probable UTI
 - b. Symptomatic UTI
3. Comparison of the number (%) of subjects over the 16-week study period with at least one:
 - a. Symptomatic or Probable UTI
 - b. Symptomatic UTI

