10.8 Analysis Methods

Summary statistics of frequencies, percentages, and 95% confidence intervals will be provided for categorical data. Means, standard deviations (SD), medians, and ranges (minimum, maximum) will be provided for continuous data. Chi-square test (Cochran-Mantel-Haenszel [CMH] methods), Fisher's exact test, or McNemar's test will be used for categorical variable comparisons and a t-test or rank-sum test will be used for continuous variable comparisons. Specifically, the following table lists the key variables to be analyzed by endpoint.

Table 1 **Analysis Variables and Methods**

Endpoint	Variable	Type	Statistics	Method
Primary	Percent of subjects with any Symptomatic/Probable UTI	Categorical	Frequency, Percent	95% confidence intervals
	Incidence of Symptomatic/Probable UTI	Categorical	Frequency, Percent	CMH
	Time to recurrence of first Symptomatic UTI	Numeric	Mean time to recurrence	Survival analysis, log rank test
Secondary	Change in vaginal microbiota (Nugent score)	Categorical	Frequency, Percent	Shift table (from Visit 1 to Visit 6), CMH
	Total Lactobacillus vaginal colonization	Categorical	Frequency, Percent	95% confidence interval at Visits 1-6
	Colonization with CTV-05	Categorical	Frequency, Percent	95% confidence interval at Visits 1-6

Endpoint	Variable	Type	Statistics	Method
	Total E. coli vaginal colonization	Categorical	Frequency, Percent	95% confidence interval at Visits 1-6
	Change in vaginal microbiota (DNA Amplification)	Categorical	Frequency, Percent	CMH 95% confidence interval
	H2O2, lactic acid, cytokines	Numeric	Medians, Percentiles	Wilcoxon rank-sum test
	Adverse Events, Serious Adverse Events, Symptoms, and signs of irritation on pelvic examination	Categorical	Frequency, Percent	Fisher's exact test may be used for selected AE preferred terms, symptoms or findings

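### The episode-count analysis for primary objective 2 gives a CMH p-value with no between-arm effect size and no allowance for incomplete follow-up

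*Combined protocol and SAP*

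**What the plan says.** Section 3.2.1 lists three parts of the primary objective: the percentage of women with at least one recurrence, incidence, and time to recurrence. The second is "To evaluate the efficacy of LACTIN-V, compared to placebo, in reducing the incidence of symptomatic UTI". Section 10.1 words the endpoint as "UTI incidence over the 16-week study period in the LACTIN-V treatment group (Group A) as compared to the placebo group (Group B) of" two outcomes: symptomatic or probable UTI, and symptomatic UTI.

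Section 10.9.2 assigns the analysis. Episodes per subject are summarised by arm, "Number and percent of subjects with 0, 1, 2, ..., n episodes will be displayed by treatment group", and "P-value will be calculated by CMH methods to evaluate any difference between the treatment groups". The Table 1 row in section 10.8 reads "Incidence of Symptomatic/Probable UTI Categorical Frequency, Percent CMH". No scores or strata are named for the CMH test. Nothing in section 10 gives a person-time denominator, an episode rate, a between-arm effect measure for counts, or a rule for women whose follow-up is cut short.

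**The concern.** Incidence is the only part of the primary objective in which repeat episodes count. The comparison of episode counts ends in a p-value, so a reader of the results would learn whether the arms differ but not by how much, or how precisely that is known.

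The test also takes each woman's count at face value whatever her time in the study. The protocol makes unequal time likely. Women may leave at any point and are not replaced (6.2.1.5), exit before Visit 6 is provided for (6.5), and the MITT cohort needs only one dose (10.7). If one arm loses more women, its counts fall for that reason alone. More loss on LACTIN-V would look like benefit; more loss on placebo would hide benefit.

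**Working it through.** **Step 1: the plan's own figure.** None is given for this test. The power statement in 10.4 concerns the proportion of women with a recurrence. Taking 40% vs 20%, 125 per arm and two-sided 5% (the level is not stated, so this is an assumption), power = Φ[(0.20·√125 − 1.96·√(2·0.30·0.70)) / √(0.40·0.60 + 0.20·0.80)] = Φ[(2.236 − 1.270)/0.632] = Φ(1.53) = 93.7%. The stated figure of more than 80% holds and is not in question here.

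**Step 2: do other sections fill the gap?**
- 10.9.1 gives the number and percentage with any episode, with a 95% CI. Repeat episodes are not used.
- 10.9.3 gives Kaplan-Meier and log-rank. Follow-up time is used, but only to the first episode.
- 10.9.2 uses repeat episodes, but neither follow-up time nor an effect measure.

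No section combines repeat episodes, follow-up time and an effect estimate.

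**Step 3: how drop-out moves the counts.** Express follow-up as a fraction of the full period. If a proportion d leave at a constant hazard, mean follow-up is d/(−ln(1−d)).
- d = 5%: 0.05/0.0513 = 0.975
- d = 30%: 0.30/0.3567 = 0.841
- d = 10%: 0.10/0.1054 = 0.949
- d = 25%: 0.25/0.2877 = 0.869

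With no treatment effect and drop-out of 5% vs 30%, the expected ratio of mean counts is 0.841/0.975 = 0.86 instead of 1.00. With a true rate ratio of 0.50 and drop-out of 25% placebo, 10% active, it is 0.50 × 0.949/0.869 = 0.55.

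**Step 4: effect on the tests.** Simulation assumptions: 125 per arm, mean 0.55 episodes over full follow-up on placebo, gamma-Poisson counts with dispersion 0.8, and drop-out as in step 3. Two tests were compared at two-sided 5%.
- CMH mean-score test (my reading, since no score is named): z = (ȳ₁ − ȳ₀)/√(s²·2/n), with s² the pooled variance of the counts.
- Rate model: R = Σy/Σt in each arm; z = ln(R₁/R₀)/√(V₀ + V₁), with V = Σ(y − Rt)²/(Σy)².

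| True rate ratio | Drop-out placebo / active | CMH rejects | Rate model rejects |
|---|---|---|---|
| 1.0 | 4% / 4% | about 5% | about 5% |
| 1.0 | 10% / 20% | about 6% | about 5% |
| 1.0 | 5% / 30% | about 10% | about 5% |
| 0.5 | 4% / 4% | 83% | 84% |
| 0.5 | 10% / 10% | 82% | 83% |
| 0.5 | 10% / 5% | about 80% | about 84% |
| 0.5 | 25% / 10% | about 67% | 81% |

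Repeat runs differ by about one percentage point.

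**Step 5: sensitivity to the model.** A mean of 0.55 with dispersion 0.8 implies 1 − (1 + 0.8·0.55)^(−1/0.8) = 36.6% of women with a recurrence, a little under the 40% in 10.4. A second set used Poisson counts with mean −ln(0.60) = 0.511, which matches 40%, and leaving times uniform over follow-up. The pattern is the same: under the null with 10% placebo and 30% active drop-out, CMH rejects in 9.1% and the rate model in 5.2%. With a halved rate and 30% placebo, 10% active, power is 72.9% against 87.8%. With a halved rate and 20% in both arms it is 87.3% against 88.3%.

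**The case against.** The strongest case against is that the plan does more than the bare p-value suggests, and that the distortion may never arise.

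A reader might infer that incidence is never estimated. The documents do not support that. Section 10.1 defines it over a fixed 16-week window, and 10.9.2 summarises episodes per woman by arm; with complete follow-up that summary is incidence over the window.

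A reader might also infer that there are no confidence intervals at all. Section 10.8 promises 95% intervals for categorical data, and Table 1 types incidence as categorical, so by-arm intervals for the percentages are planned. What is missing is narrower: an interval for a between-arm effect on episode counts.

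Nor does the sample-size wording "to detect a 50% reduction in UTI incidence" show that a person-time rate was intended. Section 10.4 derives it from the share of women expected to recur, and 10.9.1 estimates that share.

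On size, women who stop product are to be followed for efficacy where possible (6.2.1.2.2, 6.2.1.4), and log-rank in 10.9.3 handles censoring for first episodes. In the earlier Phase 2 trial at the University of Washington (2.2.2.2), 50 women per arm were randomised and results are given for 48 and 48, or 2/50 = 4% missing in each arm. Those are women analysed, so this is only a proxy for drop-out, but at 4% in both arms the two tests are practically the same.

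All of this stands and limits the point. It does not supply an effect size for episode counts or a rule for incomplete follow-up.

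**Conclusion.** The point holds in a limited form. For episode counts, primary objective 2 gets by-arm summaries and a CMH p-value, without a between-arm effect and interval and without allowance for shortened follow-up. The first omission matters at any level of retention.

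The second matters only if drop-out differs by arm, and the documents give no drop-out figures by arm. A reader might infer that the planned test is invalid as it stands; that is not supported. With equal drop-out its type I error is about 5% and its power is within a point or two of the rate model. At 10% vs 20% type I error is about 6%. It takes a gap such as 5% vs 30% to reach about 10%, or 25% placebo vs 10% active to lower power to about 67% against 81%. These sizes rest on the assumed event rate, dispersion, drop-out pattern and mean-score form of CMH. This is an inexpensive improvement that should be made, not a fatal fault.

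**What to change.** In 10.9.2 and the Table 1 incidence row, replace the CMH test with a negative binomial model (or Poisson with robust variance) of episode count on arm, with the log of follow-up days as offset. Report the rate ratio with its 95% CI. Keep the table of women with 0, 1, 2 and more episodes as description.

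Two definitions are needed:
- **Follow-up days:** from randomisation to last contact or Visit 6. Counts and days must stop at the same date, so state which end applies, because 10.1 speaks of 16 weeks and 10.3 places Visit 6 at Week 18.
- **Days after an episode:** 10.3 does not allow a new UTI until the prior one is confirmed resolved. Either use total follow-up days as the offset, which is simpler, or state how unresolved-episode days are removed.

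The cost is analysis wording and slightly more analysis work. Total follow-up needs only randomisation and last-contact or visit dates; removing unresolved days would also need resolution dates. Power is essentially unchanged when drop-out is equal. The model assumes that drop-out is non-informative, which the plan should state.
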